4. SELECTION AND WITHDRAWAL OF PATIENTS

Prospective waivers (exceptions) from study inclusion and exclusion criteria to allow patients to be randomized/enrolled are not granted by Teva ([Appendix C](#)).

4.1. Patient Inclusion Criteria

Patients may be included in the study only if they meet all of the following criteria:

- a. The patient is capable of giving signed informed consent.
- b. Male or female patient aged 18 to 70 years, inclusive.
- c. The patient has a diagnosis of migraine with onset at ≤ 50 years of age.
- d. The patient is in good health in the opinion of the investigators as determined by medical history, physical examination, laboratory tests, and ECG.
- e. Body weight ≥ 45 kg and body mass index (BMI) within the range 17.5 to 34.9 kg/m² (inclusive).
- f. The patient has a history of migraine (according to ICHD-3 criteria [[IHS 2013](#)]) or clinical judgment suggests a migraine diagnosis (not better accounted for by another ICHD-3 diagnosis) for ≥ 12 months prior to screening.
- g. The patient fulfills the following criteria for CM or EM in prospectively collected baseline information during the 28-day run-in period:

For patients with CM:

- Headache occurring on ≥ 15 days
- On ≥ 8 days, fulfilling any of the following:
 - ICHD-3 diagnostic criteria C and D for 1.1 Migraine without aura
 - ICHD-3 criteria B and C for 1.2 Migraine with aura
 - Probable migraine (a migraine subtype where only 1 migraine criterion is missing)
 - The patient used a triptan or ergot derivative to treat an established headache

For patients with EM:

- Headache occurring on ≥ 6 days but < 15
- On ≥ 4 days, fulfilling any of the following:
 - ICHD-3 diagnostic criteria C and D for 1.1 Migraine without aura
 - ICHD-3 criteria B and C for 1.2 Migraine with aura
 - Probable migraine (a migraine subtype where only 1 migraine criterion is missing)

- The patient used a triptan or ergot derivative to treat an established headache
- h. At the time of screening, the patient must have documented inadequate response to 2 to 4 classes of prior preventive migraine medications (as defined in [Appendix H](#)) within the past 10 years (in medical chart or by treating physician’s confirmation; see [Appendix I](#) for acceptable documentation of previous treatment failure). Inadequate response to prior preventive migraine medications (including valproic acid) is defined as: no clinically meaningful improvement per treating physician’s judgment, after at least 3 months of therapy at a stable dose considered appropriate for migraine prevention according to accepted country guidelines, or when treatment has to be interrupted because of adverse events that made it intolerable for the patient, or the medication (as defined in [Appendix H](#)) is contraindicated or unsuitable for the prophylactic treatment of migraine for the patient. The 3- month period does not apply if the drug is intolerable or contraindicated. If onabotulinumtoxinA is the previous preventive medication, at least 2 sets of injections and 3 months must have passed since the last set of injections prior to the screening visit.
- i. The patient agrees not to initiate any preventive migraine medications (as defined in [Appendix H](#)) during the run-in period, double-blind treatment period, and open-label period. At the screening visit, at least 5 half-lives of these medications must have passed since the patient has been on any migraine preventive medication as defined in [Appendix H](#).
- j. Other prescription medications not in [Appendix H](#) must have been on stable doses for at least 2 months at the screening visit with no expectation to change during the double-blind treatment period of the study.
- k. The patient demonstrated compliance with the electronic headache diary during the run-in period by entry of headache data on a minimum of 24 days cumulative during the run-in period (~85% diary compliance).
- l. Women may be included only if they have a negative serum beta-human chorionic gonadotropin (β -HCG) test at screening, are sterile, or postmenopausal. Definitions of sterile and postmenopausal are given in [Appendix E](#).
- m. Women of childbearing potential (WOCBP) whose male partners are potentially fertile (ie, no vasectomy) must use highly effective birth control methods for the duration of the study and the follow-up period (ie, starting at screening) and for 6.0 months after discontinuation of IMP (for details of WOCBP, sterile, and postmenopausal women, see [Appendix E](#)).
- n. Men must be sterile, or if they are potentially fertile/reproductively competent (not surgically [eg, vasectomy] or congenitally sterile) and their female partners are of childbearing potential, must use, together with their female partners, acceptable birth control methods for the duration of the study and for 6.0 months after discontinuation of the IMP.

- o. The patient must be willing and able to comply with study restrictions, to remain at the clinic for the required duration during the study period and to return to the clinic for the follow-up evaluations, as specified in this protocol.

4.2. Patient Exclusion Criteria

Patients will be excluded from participating in this study if they meet any of the following criteria:

- a. At the time of screening visit, patient is receiving any preventive migraine medications, regardless of the medical indication (as defined in [Appendix H](#)) for more than 5 days and expects to continue with these medications.
- b. Patient has received onabotulinumtoxinA for migraine or for any medical or cosmetic reasons requiring injections in the head, face, or neck during the 3 months before screening visit.
- c. The patient uses medications containing opioids (including codeine) or barbiturates (including butalbital/aspirin/caffeine [Fiorinal[®], Actavis plc], butalbital/paracetamol/caffeine [Fioricet[®], Cardinal Health], or any other combination containing butalbital) on more than 4 days during the run-in period for the treatment of migraine or for any other reason.
- d. The patient has used an intervention/device (eg, scheduled nerve blocks and transcranial magnetic stimulation) for migraine during the 2 months prior to screening.
- e. The patient uses triptans/ergots as preventive therapies for migraine.
- f. Patient uses non-steroidal anti-inflammatory drugs (NSAIDs) as preventive therapy for migraine on nearly daily basis for other indications. Note: Low dose aspirin (eg, 81 mg) used for cardiovascular disease prevention is allowed.
- g. The patient suffers from unremitting headaches, defined as having headaches for more than 80% of the time he/she is awake, and less than 4 days without headache per month. Daily headache is acceptable if patient has headaches 80% or less of the time he/she is awake on most days.
- h. The patient has a clinically significant hematological, cardiac, renal, endocrine, pulmonary, gastrointestinal, genitourinary, neurologic, hepatic, or ocular disease that, in the opinion of the investigator, could jeopardize or would compromise the patient's ability to participate in this study.
- i. Evidence or medical history of clinically significant psychiatric issues that, in the opinion of the investigator, could jeopardize or would compromise the patient's ability to participate in this study including major depression, panic disorder, or generalized anxiety disorder, any suicide attempt in the past or suicidal ideation with a specific plan the past two years prior to screening or current suicidal ideation as measured by eC-SSRS.

- j. History of clinically significant cardiovascular disease or vascular ischemia (such as myocardial, neurological [e.g., cerebral ischemia], peripheral extremity ischemia, or other ischemic event) or thromboembolic events (arterial or venous thrombotic or embolic events), such as cerebrovascular accident (including transient ischemic attacks), deep vein thrombosis, or pulmonary embolism.
- k. History of human immunodeficiency virus, tuberculosis, or chronic hepatitis B or C infection.
- l. Past or current history of cancer, except for appropriately treated non-melanoma skin carcinoma in the last 5 years.
- m. Pregnant or lactating female patients or female patients who plan to become pregnant during the study.
- n. Participation in a clinical study of a new chemical entity or a prescription medicine within 2 months before screening (or 3 months in case of biologics if the half-life of the biologics is unknown) or 5 half-lives, whichever is longer, or is currently participating in another study of an IMP (or a medical device).
- o. Any prior exposure to a monoclonal antibody targeting the CGRP pathway (such as AMG 334, ALD304, LY2951742, or fremanezumab).
- p. Any finding in the baseline 12-lead ECG considered clinically significant in the judgment of the investigator.
- q. Any finding that, in the judgment of the investigator, is a clinically significant abnormality, including serum chemistry, hematology, coagulation, and urinalysis test values (abnormal tests may be repeated for confirmation).
- r. Hepatic enzymes (alanine aminotransferase, aspartate aminotransferase, and alkaline phosphatase) $>1.5 \times$ the upper limit of the normal (ULN) range after confirmation in a repeat test or suspected hepatocellular damage that fulfills criteria for Hy's law at screening.
- s. Serum creatinine $>1.5 \times$ the ULN, clinically significant proteinuria, or evidence of renal disease at screening.
- t. The patient has a history of alcohol abuse during the 2 years prior to screening.
- u. The patient has a history of drug abuse during the past 2 years or drug dependence during the past 5 years.
- v. The patient cannot participate or successfully complete the study, in the opinion of their healthcare provider or the investigator, for any of the following reasons:
 - mentally or legally incapacitated or unable to give consent for any reason
 - in custody due to an administrative or a legal decision, under tutelage, or being admitted to a sanitarium or social institution
 - unable to be contacted in case of emergency

- has any other condition, which, in the opinion of the investigator, makes the patient inappropriate for inclusion in the study
- w. The patient is a study center or sponsor employee who is directly involved in the study or the relative of such an employee.
- x. The patient has been previously screen failed for the study.

4.3. Withdrawal Criteria and Procedures for the Patient

Each patient is free to withdraw from the study or discontinue from the IMP at any time, without prejudice to their continued care. Patients must be withdrawn from the IMP and/or study if any of the following events occur:

1. Patient withdraws consent or requests discontinuation from the IMP or withdrawal from the study for any reason.
2. Patient develops an illness that would interfere with his/her continued participation.
3. Patient is noncompliant with the study procedures and assessments or administration of IMPs in the opinion of the investigator.
4. Patient takes prohibited concomitant medications as defined in this protocol.
5. A female patient has a confirmation of pregnancy during the study from a positive pregnancy test.
6. The sponsor requests withdrawal of the patient.
7. Patient experiences an adverse event or other medical condition which indicates to the investigator that continued participation is not in the best interest of the patient.

Patients should be treated with standard of care after withdrawal from or termination of the study as appropriate.

Investigators should attempt to obtain information on patients in the case of withdrawal from the study or discontinuation from IMP. Results of any evaluations and observations, together with a narrative describing the reason(s) for withdrawal from the study or discontinuation from IMP, must be recorded in the source documents. The case report form (CRF) must document the primary reason for withdrawal from the study or discontinuation from IMP.

For information regarding how the study will define and address lost to follow-up patients to help limit the amount and impact of missing data, see [Appendix F](#).

If the reason for withdrawal from the study or discontinuation from IMP is an adverse event and/or clinically significant abnormal laboratory test result, monitoring will be continued as applicable (eg, until the event has resolved or stabilized, until the patient is referred to the care of a health care professional, or until a determination of a cause unrelated to the IMP or study procedure is made). The specific event or test result (including repeated test results, as applicable) must be recorded both on the source documentation and in the CRF; both the adverse events page and the relevant page of the CRF will be completed at that time.

The investigator must inform the Sponsor or delegate as soon as possible of each patient who is being considered for withdrawal due to adverse events. Additional reports must be provided when requested.

If a patient is withdrawn from the study or discontinues IMP for multiple reasons that include also adverse events, the relevant page of the CRF should indicate that the withdrawal was related to an adverse event. An exception to this requirement will be the occurrence of an adverse event that in the opinion of the investigator is not severe enough to warrant discontinuation but that requires the use of a prohibited medication, thereby requiring discontinuation of the patient. In such a case, the reason for discontinuation would be “need to take a prohibited medication”, not the adverse event.

In the case of patients lost to follow-up, attempts to contact the patient must be made and documented in the patient’s medical records and transcribed to the CRF.

All protocol-specified procedures/assessments should be performed at the EOT/ early withdrawal visit (see [Table 2](#)). Patients who withdraw from the study will be instructed to come back to the site for blood sample collection for the purpose of evaluating ADA 6.0 months (180 days [the approximate equivalent of 5 half-lives]) after their last dose of study drug. A patient should only be designated as lost to follow up if the site is unable to establish contact with the patient after 3 documented attempts via 2 different methods (phone, text, e-mail, certified letter, etc).

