1.3.1.2.2. Consequences of Calcitonin Gene-Related Peptide Inhibition

Because CGRP is a vasodilator, the following 4 major cardiovascular effects are of potential concern with CGRP inhibition, a priori: medication-induced hypertension, counterbalancing the effect of anti-hypertensive drugs that have vasodilatory properties, inhibition of stress- (or ischemia-) induced vasodilation, and impairment of cardioprotective mechanisms. Extensive research conducted with the CGRP receptor antagonists has not identified relevant safety cardiovascular concerns in humans. Dedicated studies conducted in monkey and in humans using fremanezumab have not identified clinically relevant changes in heart rate, blood pressure, or other cardiovascular parameters. No relevant cardiovascular event has been seen in the completed studies.

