
A secondary objective of the study is to evaluate the safety and tolerability of fremanezumab administered as monthly and quarterly sc injections to adult patients with migraine with inadequate response to 2 to 4 classes of prior preventive treatments as compared with placebo
	
Secondary safety/tolerability endpoints:
 
 ● occurrence of adverse events throughout the study ● clinical laboratory (serum chemistry, hematology, coagulation and urinalysis) test results at specified time points ● vital signs (systolic and diastolic blood pressure, oral temperature, and pulse rate) measurements at each visit. Note: In addition, oxygen saturation and respiratory rate will be measured in cases of suspected anaphylaxis and severe hypersensitivity ● 12-lead ECG findings at specified time points ● use of concomitant medication for adverse events during the study ● number (%) of patients who did not complete the study due to adverse events ● clinically significant changes in physical examinations, including body weight ● occurrence of severe hypersensitivity/anaphylaxis reactions ● suicidal ideations and behaviors as measured by the eC-SSRS

ECG=electrocardiogram; eC-SSRS= electronic Columbia-Suicide Severity Rating Scale; Test; sc=subcutaneous.

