Each study drug shipment will include a packing slip listing the contents of the shipment, drug return instructions, and any applicable forms.

Each investigator is responsible for ensuring that deliveries of study drug and other study materials from Teva are correctly received, recorded, handled, stored, accounted for, and used in accordance with this protocol. In addition, each investigator is responsible for ensuring that study drug and other materials from Teva are correctly, safely, and properly disposed of in accordance with local regulations.

A record of study drug accountability (ie, study drug and other materials received, used, retained, returned, or destroyed) must be prepared and signed by the principal investigator or designee, with an account given for any discrepancies.

APPENDIX H. MEDICATIONS TO EVALUATE PATIENT QUALIFICATION FOR INADEQUATE RESPONSE TO PRIOR TREATMENT AND DISALLOWED DURING THE RUN-IN TREATMENT PERIOD, AND FOLLOW-UP PERIOD

(Martelletti et al 2014)

The use of the medications listed below on a daily basis for other indications is disallowed for the duration of the study.

- beta-blockers: propranolol, metoprolol, atenolol, and bisopropol
- anticonvulsants: topiramate
- tricyclics: amitriptyline
- calcium channel blocker: flunarizine
- angiotensin II receptor antagonist: candesartan
- onabotulinumtoxinA
- valproic acid

Any of the listed medications are allowed if given as topical or eye drops.

Other medications in the same classes but not included in this list are allowed.

Definition of Inadequate Response to Prior Treatment

- Patients must have documented inadequate response (in medical chart or by treating physician's confirmation) to 2 to 4 classes of prior preventive medications from the list above regardless of which class the medication belongs to.
- Inadequate response is defined as: no clinically meaningful improvement per treating physician's judgment, after at least 3 months of therapy at a stable dose considered appropriate for migraine prevention according to accepted country guidelines, or when treatment has to be interrupted because of adverse events that made it intolerable by the patient or the drug is contraindicated or not suitable for the patient. The 3 month period does not apply if the drug is intolerable or contraindicated or not suitable for the patient.

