6.2.3.2. Analysis with Multiple Imputation Method

Sensitivity analysis will be performed by imputing missing migraine days of months 1-3 using multiple imputation method. The data will be processed by the following steps.

- If a patient has partial electronic headache diary data (ie, <28 days) for a month, that month’s value will be considered missing before the MI procedure.
- For the patients in the fremanezumab treatment group who are early terminated with reasons of adverse event or lack of efficacy, they will be assigned to placebo group so their missing values will be imputed using data from the placebo treated patients
- Run SAS PROC MI procedure to create 100 complete datasets.

The following SAS code pertains to the MI analysis:

```
PROC MI DATA=XXX SEED=SEED OUT=MI_OUT NIMPUTE=100
MAXIMUM=. . . . . 28 28 28 MINIMUM=. . . . . 0 0 0;
CLASS TREAT GENDER REGION TRTFAIL MIGCLASS;
FCS REG (AVALMI1=TREAT GENDER REGION TRTFAIL MIGCLASS
BASE YOD/DETAILS) NBITER=100;
FCS REG (AVALMI2=TREAT GENDER REGION TRTFAIL MIGCLASS
BASE YOD AVALMI1/DETAILS) NBITER=100;
FCS REG (AVALMI3=TREAT GENDER REGION TRTFAIL MIGCLASS
BASE YOD AVALMI1 AVALMI2/DETAILS) NBITER=100;
VAR TREAT GENDER REGION TRTFAIL MIGCLASS YOD BASE
AVALMI1 AVALMI2 AVALMI3;
RUN;
```

- Within each imputed data set, for a patient who has partial, say X ($X < 28$) days , electronic headache diary data in a month, the monthly value will be replaced by
- $\sum(\text{observed days}) + (28 - X) * \text{imputed value} / 28$
- The monthly average number of migraine days *during the 12-week double-blind period* after the 1st dose of study drug will be the average of month 1, month 2 and month 3 values.

Each dataset will be analyzed using the same ANCOVA model as described in Section 6.2.2. The LS means and standard errors from each analysis will be output to a SAS data set. SAS MIANALYZE procedure will be used to generate the final LS means (\pm SE) for the treatment groups and the treatment differences (fremanezumab - placebo) as well as p-values associated with treatment differences. Ninety-five percent CIs for the LS means differences between each

Statistical Analysis Plan

fremanezumab treatment group (monthly dose and quarterly dose) and placebo will be constructed.

```
ODS OUTPUT DIFFS=MIXED_OUT;  
PROC MIXED DATA=UPDATED_MI_OUT METHOD=REML;  
BY _IMPUTATION_;  
CLASS TREAT GENDER REGION TRTFAIL MIGCLASS;  
MODEL CHG=BASE YOD TREAT GENDER REGION TRTFAIL MIGCLASS  
TREAT*MIGCLASS;  

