8.10. Concomitant Medications or Therapies

Concomitant therapies and medications, including medications that are taken on an as needed basis and occasional therapies, will be monitored during the study. Details of prohibited medications may be found in Section 5.6 of the study protocol. All concomitant medications will be coded using the WHO Drug.

The incidence of concomitant therapies and medications will be summarized using descriptive statistics by therapeutic class category and preferred term. Patients are counted only once in each therapeutic class and only once in each preferred term category. Concomitant therapies and medications will include all medications up to the end of study as defined in the study protocol.

The subset of concomitant pain medication and medication or therapy for migraine/headache will be summarized by the following indication categories.

- migraine/headache preventive medication
- triptans and ergots for migraine/headache
- triptans and ergots for reasons other than migraine/headache
- butalbital for migraine/headache
- butalbital for reasons other than migraine/headache
- NSAIDs for migraine/headache
- NSAIDs for reasons other than migraine/headache
- opioids for migraine/headache

Statistical Analysis Plan

- opioids for reasons other than migraine/headache
- preventive medication for other reasons

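### A withdrawal triggered by an adverse event that needs a prohibited drug is recorded under another reason, so it can drop out of the adverse-event non-completion endpoint

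*Protocol*

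**What the plan says.** Protocol 4.3 first sets a general rule: when an adverse event is among several reasons for leaving, "the relevant page of the CRF should indicate that the withdrawal was related to an adverse event". It then makes one exception, for an event that is "not severe enough to warrant discontinuation but that requires the use of a prohibited medication, thereby requiring discontinuation of the patient". The protocol is explicit about what is recorded: "In such a case, the reason for discontinuation would be “need to take a prohibited medication”, not the adverse event".

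Two analyses depend on the recorded reason:

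- Protocol 2.1, Table 1, names as a secondary safety/tolerability endpoint the "number (%) of patients who did not complete the study due to adverse events". SAP 1.1 repeats it, and SAP 5.2 tabulates withdrawals from treatment and from the study by reason.
- SAP 6.2.3.2 treats fremanezumab patients as placebo patients for multiple imputation if they were "early terminated with reasons of adverse event or lack of efficacy".

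The prohibited list in Protocol Appendix H includes four named beta-blockers and "angiotensin II receptor antagonist: candesartan". It covers daily use for indications other than migraine, but it allows unlisted drugs of the same classes. Protocol 1.3.1.2.2 lists "medication-induced hypertension, counterbalancing the effect of anti-hypertensive drugs that have vasodilatory properties" among the theoretical effects of CGRP inhibition.

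Table 1 also names the use of concomitant medication for adverse events as a secondary endpoint. SAP 8.10 summarizes concomitant drugs by class and preferred term, and adds: "The subset of concomitant pain medication and medication or therapy for migraine/headache will be summarized by the following indication categories".

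**The concern.** In the excepted case the adverse event starts the chain that ends in withdrawal, yet the event is removed from the reason. The exception can only lower the count of non-completion due to adverse events, never raise it. Whether it applies rests on the investigator's judgment of severity. The events it can reach are those whose treatment is an Appendix H drug, and these include some blood-pressure events. Hypertension is not an adverse event of special interest (Protocol 7.1.7, SAP 8.3), so no dedicated summary restores the link.

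If fremanezumab caused such events, the between-arm comparison on this endpoint would be pulled toward no difference. In the imputation analysis, the recoded fremanezumab patient's missing months would be filled in as if the patient were still on active treatment.

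**Working it through.** **No plan figure to reproduce.** The documents give no expected rate of adverse-event withdrawal, prohibited-drug withdrawal or hypertension. Protocol 9.1 assumes 12% discontinuation from all causes, 0.12 × 268 = 32 patients per arm, and does not split it by reason.

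**Where a recoded patient appears.** Take an event that is treated with a listed drug, is judged not severe enough to stop, and is followed by withdrawal.

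- *Disposition by reason (SAP 5.2):* appears under prohibited medication, not under adverse event.
- *Adverse-event tables (SAP 8.3):* appears. Protocol 7.1.2 requires every event to be recorded, with the treatment given and the action taken on study drug.
- *Adverse events causing withdrawal from treatment (SAP 8.3):* undetermined. The SAP does not say whether the source is the action-taken field or the disposition reason. The case can appear in the first and would not appear in the second.
- *Vital signs (SAP 8.7):* values are summarized. The significance flag needs systolic pressure of at least 180 mm Hg with a rise of at least 20, or diastolic of at least 105 with a rise of at least 15. Treated hypertension below these levels is not flagged.
- *Concomitant drugs (SAP 8.10):* appears by class and term, and plausibly in the last listed row, for preventive drugs used for other reasons. No row is limited to drugs given for an adverse event.
- *Multiple imputation (SAP 6.2.3.2):* keeps the fremanezumab label.

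**Absolute effect.** With 268 planned patients per arm, and the ITT set as denominator (SAP 5.2):

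- one patient, one arm: 1/268 = 0.37 percentage points
- one patient, both active arms pooled: 1/536 = 0.19 percentage points

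**Relative effect.** Let k be the patients still counted under adverse event and m the number recoded. The share of the true count that is lost is m/(k + m). Assume k = 3 to 8, a reported rate of 3/268 = 1.1% to 8/268 = 3.0%.

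- m = 1: 1/4 = 25% at k = 3; 1/9 = 11% at k = 8
- m = 2: 2/5 = 40% at k = 3; 2/10 = 20% at k = 8

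Here k is the number still counted. If 3 to 8 were the true number, one recoded patient would be 1/3 = 33% to 1/8 = 12.5% of it.

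**How many could be recoded.** By assumption only: true frequencies of 0.1%, 0.5%, 1% and 2% would give 0.3, 1.3, 2.7 and 5.4 patients per arm of 268.

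**Imputation.** Suppose one recoded patient has all three months missing, and the wrong arm label shifts the imputed value by the full design difference of 1.8 days (Protocol 9.1). The arm mean then moves by 1.8/268 = 0.007 days.

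**The case against.** The strongest reply is that the rule is prespecified, is judged under blinding and applies equally to all arms. It separates intolerance of the drug from withdrawals forced by the medication ban. Deleting it would count, as driven by adverse events, withdrawals for events that the investigator did not think warranted stopping. That stands, and it is why the recorded reason should be kept and a second count added beside it.

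Four stronger readings are tempting, and the documents do not support them:

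- *The safety reporting omits the cardiovascular events of most interest.* It does not. The events stay in three sets of tables. Protocol 1.3.1.2.2 calls these effects a concern in principle and reports that studies to date found no clinically relevant blood-pressure change.
- *Treated hypertension generally falls under the exception.* The route is narrow. It needs a listed drug and a judgment that the event is not severe enough to stop. Events severe enough to stop are still counted.
- *The patient must leave.* Protocol 4.3 requires or presumes it. But Protocol 5.6 allows drugs to treat adverse events, and Appendix C, which lists prohibited-drug use as a possible deviation, lets the sponsor keep the patient in the study.
- *SAP 8.10 shows only headache and pain drugs.* Its last row covers preventive drugs used for other reasons. What is missing is a table restricted to drugs given for adverse events.

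**Conclusion.** The point holds in a narrow form. As written, Protocol 4.3 moves some withdrawals triggered by adverse events out of a named secondary endpoint, in one direction only, and no planned table is certain to restore them. The absolute effect is 0.37 percentage points per recoded patient per arm. The relative effect of 11-25% for one patient rests entirely on the assumption that 3 to 8 patients per arm are still counted. The number recoded is unknown and, given the short drug list and the allowance for unlisted drugs, probably small.

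A bias between arms needs a further assumption, that such events are more frequent on fremanezumab; the documents do not show this. The imputation effect is close to nil and touches one sensitivity analysis, not the primary one. This is a cheap improvement to reporting and does not threaten the trial's conclusions.

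**What to change.** Keep the recorded reason as it is and make these changes in the SAP before the first interim database lock:

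1. In SAP 5.2 and 8.3, add a by-arm count of non-completion triggered by adverse events. It should combine withdrawals recorded as adverse event with those recorded as prohibited medication where the drug was needed to treat a recorded adverse event. State that the table of adverse events causing withdrawal from treatment uses the action-taken field.
2. Add the same flag to the list of reasons in SAP 6.2.3.2.
3. In SAP 8.10, add a by-arm summary of concomitant drugs whose recorded indication is an adverse event, so that this secondary endpoint is actually produced.

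The data are already collected: Protocol 5.6 records the indication and dates of each drug, and Protocol 7.1.2 the treatment given for each event. The cost is one extra row, one extra table and a derived flag. The adverse-event non-completion figure may rise slightly. None of this changes who is withdrawn or how an event is treated.

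Separately, Protocol 4.3, 5.6, Appendix C and Appendix H differ on whether a patient given a listed drug for an adverse event must leave. They also differ on the period: Section 5.6 refers to run-in and double-blind treatment, Appendix H to the whole study. These passages must be reconciled.
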